SUA is a product of XO activation. Analysis of the NHANES database found an elevated SUA prevalence of 21.2% in men and 21.6% in women¹⁷. Elevated SUA is associated with increased morbidity in patients with hypertension^{18, 19}, CVD and stroke²⁰, chronic kidney disease (CKD) and insulin resistance²¹. In the Framingham Heart Study, SUA was shown to be independently associated with aortic stiffness²², particularly in women, as also reported by others²³⁻³⁰. In pre-hypertensive subjects, elevated SUA was related to a higher risk of developing hypertension in women than in men³¹. The presence of diabetes significantly increases the risk of arterial stiffness in women³². Elevated uric acid (UA) and XO activation can result in chronic inflammation, endothelial dysfunction and increased oxidative stress, key events in the pathogenesis of stiffness^{33, 34}. Diet is the main driver of SUA in Western societies. Fructose supplementation elevates SUA in a dose-dependent manner³⁵. Reducing SUA with allopurinol, an XO inhibitor, reduces arterial stiffness^{36, 37} but whether reducing SUA, by either drug or diet, improves arterial stiffness in T2D subjects is unknown. Importantly, the differential effects of treatment on T2D men and women have not been tested. The proposed study will bridge this knowledge gap.

Distinct contributions of XO activity and SUA. High SUA levels can damage proteins and other macromolecules through mechanisms related to oxidative stress and inflammation as XO simultaneously generates both UA and reactive oxygen species³⁸. In the vasculature, elevated UA has been shown to increase expression of inflammatory molecules such as C-reactive protein (CRP)^{39, 40}, as well as production of reactive oxygen species^{41, 42} with parallel decreases in nitric oxide (NO) production^{41, 43}. Perez-Pozo et al. suggested that the observed benefits of allopurinol treatment on blood pressure may be the result of either reductions in the deleterious effects of SUA, or from reductions in systemic inflammation following XO inhibition⁴⁴. Consequently, in this proposal we will assess whether XO inhibition, and its direct effects on endothelial function, oxidative stress and inflammation, is superior to dietary UA reduction in improving arterial stiffness.

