In another recent fructose restriction/weight loss intervention in middle-aged adults, obese women showed a significant improvement in PWV, while men did not (Figure 4A). Relevant to this proposal, we found that PWV correlated with SUA in women after 4 weeks of weight loss (Figure 4B). TNF α and UA were the only variables that predicted $PWV = 3.604 + (0.270*UA) + (0.132*TNF\alpha)$, $r = 0.712$, $p = 0.0025$ following the weight loss in women, suggesting that SUA is a modifiable risk factor in the development of arterial stiffening in women. In another preliminary study, exposure to high glucose and high UA increased production of inflammatory markers in cultured human aortic endothelial cells

(Figure 5). Data from our basic and human studies complement growing epidemiological evidence that hyperuricemia in women is related to increased arterial stiffness, putting women at a high risk for CVD. We propose that the sexual dimorphism in arterial stiffness associated with T2D is mediated, in part, by sex-dependent effects of UA and XO activation.

B. Summary of Study Objectives

We will accomplish the following specific aims:

Aim 1: To determine if sex-related differences exist in the relationship between SUA levels and arterial stiffness (via cfPWV) in age-matched T2D men and women, and to what degree these differences are related to augmented oxidative stress, inflammation and endothelial dysfunction. Hypothesis: The relationship between arterial stiffness and elevations in SUA/augmented oxidative stress/endothelial dysfunction/increased inflammatory marker activity seen in T2D women will be weaker or absent in men.

Aim 2: To assess whether XO inhibition is superior to dietary-induced SUA reduction in ameliorating arterial stiffness in T2D subjects. Hypothesis: Although we expect XO inhibition to have the greatest impact, we posit that SUA reduction by either strategy will lead to more improvement in endothelial function and stiffness.

As shown in **Figure 6**, this project has three parts and each subject will participate in only one part. These separate treatment arms are combined into one IRB protocol because they will test an integrated hypothesis regarding uric acid and arterial stiffness in a similar population with identical procedures.

Part 1: Diet treatment

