Subjects who are eligible following the CRC screening visit will be formally consented for the specific arm of the study they are participating in (the isocaloric fructose restriction arm, the allopurinol/placebo treatment arm, or the hypocaloric fructose restriction arm of this project) before their baseline visit. Formal consenting up to 1 hour and during that process, 1) the subject will be asked to describe, in their own words, what the baseline visit will be like, and 2) the subject (in either of the fructose restriction arms) is given a three-day food record and instructed on how to fill it out. They will be provided with the study details. Review of the consent form will occur with study personnel in a quiet, unhurried setting. Comprehension will be assessed by asking the subject to explain the study in their own words. Participants will have adequate opportunity to review the informed consent and to ask any questions they may have about the research protocol, compensation, risks, and benefits of taking part in the study.

V. INCLUSION AND EXCLUSION CRITERIA

Inclusion criteria:

- 1) Men and women with BMI 25.1-50 kg/m², who are 40-75 years of age at randomization.
- 2) T2D diagnosed > 3 months ago. Patients with T2D will be classified based on physician diagnosis.
- 3) No vulnerable populations (e.g., prisoners, pregnant, children) will be enrolled.

Exclusion criteria for part 1 and part 2 of the study:

- 1) Serum uric acid < 5.5 mg/dL
- 2) Habitual diet containing low amount of sugars < 5% of total energy intake
- 3) Recent CVD event (stroke, heart failure hospitalization, revascularization or acute coronary event in the last 12 months), abnormal thyroid tests or chronic liver disease, stage IV renal disease (GFR <30) and hyperparathyroidism.
- 4) Use of azathioprine
- 5) Active cancer
- 6) Autoimmune diseases

- 7) Excessive alcohol consumption (>14 drinks/week for men, >7 drinks/week for women)
- 8) Current tobacco use
- 9) Bodyweight change $\geq 10\%$ within the last 6 months
- 10) History of gout or uncontrolled hypertension
- 11) A1C > 10.0
- 12) Pregnancy or lactation in women (or women not using contraceptives)

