Medications for glucose control (insulin, metformin, gliptins, GLP-1 agonists, sulfonylureas, sodium glucose co-transporter inhibitors), antihypertensives, hormone replacement therapy, antidepressants, anticoagulants, or statins, will be considered during recruitment, analyses (e.g., using covariate analysis) and interpretation.

Exclusion criteria for hypocaloric low-fructose diet intervention (part 3):

- 1) Habitual diet containing low amount of sugars < 5% of total energy intake
- 2) Recent CVD event (stroke, heart failure hospitalization, revascularization or acute coronary event in the last 12 months), abnormal thyroid tests or chronic liver disease, stage IV renal disease (GFR <30) and hyperparathyroidism.
- 3) Use of azathioprine
- 4) Active cancer
- 5) Autoimmune diseases
- 6) Excessive alcohol consumption (>14 drinks/week for men, >7 drinks/week for women)
- 7) Current tobacco use
- 8) Bodyweight change $\geq 10\%$ within the last 6 months
- 9) History of gout or uncontrolled hypertension
- 10) Pregnancy or lactation in women (or women not using contraceptives)

Medications for glucose control (insulin, metformin, gliptins, GLP-1 agonists, sulfonylureas, sodium glucose co-transporter inhibitors), antihypertensives, hormone replacement therapy, antidepressants, anticoagulants, or statins, will be considered during recruitment, analyses (e.g., using covariate analysis) and interpretation.

VI. NUMBER OF SUBJECTS

Sample size calculations are based primarily on satisfying the requirements of Aim 2, i.e. to show that XO inhibition and fructose restriction reduce PWV, and that these interventions are more effective in women than in men. Calculations are based on the paired *t*-test for pre- to post-treatment change, and independent *t*-tests for comparisons between treatment arms. In both cases, we assume an alpha of .05 and a two-sided alternative.

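### Aim 2 asks whether XO inhibition beats diet, but Section VI sizes only each treatment's own PWV change, and the text does not say whether drug-versus-diet allocation is random

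*Combined protocol and SAP*

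**What the plan says.** **The question.** Section I.B gives Aim 2 as "To assess whether XO inhibition is superior to dietary-induced SUA reduction in ameliorating arterial stiffness in T2D subjects". Its hypothesis reads "Although we expect XO inhibition to have the greatest impact, we posit that SUA reduction by either strategy will lead to more improvement". Section I.A says the study will assess whether XO inhibition "is superior to dietary UA reduction in improving arterial stiffness".

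**The sizing.** Section VI opens with "Sample size calculations are based primarily on satisfying the requirements of Aim 2", then explains that aim as "to show that XO inhibition and fructose restriction reduce PWV, and that these interventions are more effective in women than in men". It bases the calculations on the paired t-test for change and independent t-tests between arms, two-sided at 0.05. Table 2 has four rows: allopurinol 0.6 m/s (9 subjects for 90% power, 7 for 80%) and low fructose 0.5 m/s (13 and 10). All carry 0.4 m/s, labelled as an SE of the change. Planned enrolment is 40 diet, 40 allopurinol and 20 placebo, half of each sex. Section III.A allows for 10% dropout.

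**The allocation.** Section VII says subjects are assigned to one of three arms. It describes randomisation, 2:1 in permuted blocks, only inside the medication arm; diet subjects are recruited. Section VII.A has staff discuss with an eligible subject whether they wish to consent to one of the studies. Under Section IV.B subjects "will be formally consented for the specific arm of the study they are participating in". Inclusion criterion 1 in Section V, which covers all parts, says "who are 40-75 years of age at randomization". Figure 7, captioned as the pathway into the arms, is not shown.

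**The analysis.** Section V says medications "will be considered during recruitment, analyses (e.g., using covariate analysis) and interpretation", and Section VII.F mentions estrogen as a covariate. Neither is tied to the drug-diet contrast, and no analysis is specified for it.

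**The concern.** Two things are at stake.

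**Attribution.** If subjects or staff choose between drug and diet, the contrast mixes the treatment effect with differences between the people who enter each part. A larger PWV fall on allopurinol could not then be put down to XO inhibition alone, which is what Aim 2 wants to conclude.

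**Interpretation.** Section VI reads as if Aim 2 has been powered, but the comparison that Aim 2 names has no target difference. A reader of a non-significant result cannot tell what it excludes and may take it for equivalence. Table 2 does not help, because its one measure of variability has an unclear meaning.

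**Working it through.** **1. Reproduce Table 2.** Inputs from Section VI: differences of 0.6 and 0.5 m/s, variability 0.4, two-sided alpha 0.05, power 90% and 80%.

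Two-group normal formula, n per group = 2(z0.975 + zpower)²(SD/δ)². The squared sums are (1.960 + 1.282)² = 10.507 and (1.960 + 0.842)² = 7.849.

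- 0.6 m/s, 90%: 2 × 10.507 × (0.4/0.6)² = 9.34
- 0.6 m/s, 80%: 2 × 7.849 × (0.4/0.6)² = 6.98
- 0.5 m/s, 90%: 2 × 10.507 × (0.4/0.5)² = 13.45
- 0.5 m/s, 80%: 2 × 7.849 × (0.4/0.5)² = 10.05

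Rounded to the nearest integer, these are the printed 9, 7, 13, 10. The one-group formula (z0.975 + zpower)²(SD/δ)² with SD = 0.4 × √2 = 0.566 is algebraically identical and gives the same four values. The printed sizes therefore cannot separate a two-group SD of 0.4 from a one-group SD of change of 0.566.

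**2. Compare with the tests that Section VI names.**

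| Method | 0.6, 90% | 0.6, 80% | 0.5, 90% | 0.5, 80% |
|---|---|---|---|---|
| Printed | 9 | 7 | 13 | 10 |
| Exact paired t, SD 0.4 | 7 | 6 | 9 | 8 |
| Exact paired t, SD 0.566 | 12 | 10 | 16 | 13 |
| Exact independent t, SD 0.4, per group | 11 | 9 | 15 | 12 |

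None of the t-test rows matches. If 0.4 were literally an SE, the standardised effect for 0.6 m/s would be 0.6/0.4 = 1.5 and power about Φ(1.5 − 1.96) = 0.32. For 0.5 m/s it would be Φ(1.25 − 1.96) = 0.24. Those are far from the stated 80% and 90%.

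**3. Precision for drug versus diet.** Completers: 40 × 0.9 = 36 per arm and 20 × 0.9 = 18 per sex per arm. Two-sample t-test, two-sided 0.05, noncentrality δ/(SD√(2/n)), df = 2n − 2. The difference detectable with 80% power is about 2.84 standard errors at n = 36 and 2.88 at n = 18.

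- SD 0.4, n = 36: SE = 0.4 × √(2/36) = 0.0943, detectable 0.268 m/s
- SD 0.4, n = 18: SE = 0.4 × √(2/18) = 0.1333, detectable 0.385 m/s
- SD 0.566, n = 36: SE = 0.1333, detectable 0.379 m/s
- SD 0.566, n = 18: SE = 0.1886, detectable 0.544 m/s
- SD 0.8 (an assumption, to show the range): 0.536 m/s at n = 36 and 0.769 m/s at n = 18

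The 95% CI half-width at 36 v 36 is 1.994 × SE: 0.19 m/s (SD 0.4) or 0.27 m/s (SD 0.566).

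Power at 36 v 36 for true differences of 0.2 and 0.4 m/s is 0.553 and 0.987 (SD 0.4), or 0.316 and 0.841 (SD 0.566).

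**4. The randomised contrast.** Allopurinol against placebo for 0.6 m/s:

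- 36 v 18: power >99% (SD 0.4), 95% (SD 0.566), 72% (SD 0.8)
- within a sex, 18 v 9: 94%, 70% and 42%

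**The case against.** The allocation point rests on what can be read. Figure 7 may show a random step, and inclusion criterion 1 speaks of randomisation. A reader might infer from the discussion in Section VII.A that subjects choose their arm; the text neither says so nor excludes random allocation. This part is therefore conditional. The plan also deserves credit for one exclusion list shared by Parts 1 and 2, identical procedures and a blinded vascular assessor. These narrow the scope for bias but do not make the groups exchangeable.

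A reader might infer that Section VI prescribes an unadjusted t-test for drug versus diet. It does not: the t-tests are the stated basis of the size calculation, and the plan elsewhere points to covariate analysis. What stands is that no analysis is specified for this contrast.

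A reader might subtract Table 2's effects, 0.6 − 0.5 = 0.1 m/s, and conclude that the trial has about 20% power at 40 v 40 and needs 252 per arm. The plan expects diet to do less well but never sets 0.1 m/s as a target, so those figures are illustrative only. Against the 0.6 m/s that it calls clinically meaningful, 36 v 36 is adequate under both SD readings.

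Finally, a reader might call 0.4 simply a mislabelled SD of change. The printed sizes fit 0.566 equally well, and the source of the figure cannot be seen here, so only the sponsor can say what it is.

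**Conclusion.** The concern holds as a mismatch between Aim 2 and Section VI, with a conditional point about attribution. It should be fixed but is not fatal. The sizing part stands whether or not allocation is random: the drug-diet question has no stated difference, power or analysis, and Table 2's sizes match neither named test at the printed 0.4. The comparison is sound for a large gap between drug and diet and weak for a small one. The detectable differences assume an SD of change of 0.4 or 0.566 m/s, equal in both arms, and 10% dropout; they grow in proportion to the SD. The attribution part applies unless allocation between Parts 1 and 2 is random. The allopurinol-placebo comparison is randomised in either case, but its power within each sex depends heavily on the SD.

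**What to change.** 1. **Section VI.** Stop stating that the size satisfies Aim 2's superiority question. Say what 0.4 is (SE, per-visit SD or SD of change) and which test was used, and correct the Table 2 sizes or powers to match that test. Add, for example: *After 10% dropout, the smallest drug-diet difference detectable with 80% power by a two-sample t-test is about 0.27 m/s (36 v 36) and 0.385 m/s within a sex (18 v 18) if the SD of change is 0.4 m/s, or about 0.38 and 0.54 m/s if it is 0.566 m/s.*
2. **Aim 2 and Section VII.** State in the text how subjects are allocated between Parts 1 and 2. Unless this is random, word Aim 2 as estimating the non-randomised difference in 6-month cfPWV change between XO inhibition and dietary SUA reduction. Name allopurinol against placebo as the randomised evidence for an XO-inhibition effect. If allocation is random, Aim 2's wording can stay.
3. **Analysis.** Specify an ANCOVA of 6-month cfPWV on arm and baseline cfPWV, with a short covariate list fixed in advance (for example age, sex and baseline SUA). Keep medications and estrogen for a sensitivity analysis: Section V lists too many drug classes to enter singly with about 72 completers. Report a 95% CI and state that a non-significant result is not read as equivalence.

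**Cost.** If allocation is not random, the trial gives up an unqualified superiority claim for drug over diet. The model uses a few degrees of freedom. There are no extra patients or visits and no change to allocation.

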The sample size calculations shown in **Table 2** are derived from the literature as follows: De Angelis *et al* have shown that in men, T2D does not increase PWV in age- and BMI-matched men without T2D ³². By contrast, in women, T2D significantly increases PWV compared to women without T2D and importantly, compared to men with T2D. Any reduction in PWV represents a significant reduction in cardiovascular risk ⁷. However, with 6 months of allopurinol treatment, we have chosen a sample size to be able to detect a reduction in PWV of 0.6 m/s, which Ng *et al* showed to be clinically meaningful ⁶⁸. Nine subjects per group (9 men and 9 women) completing the allopurinol arm will allow for 90% power to detect a change of 0.6 m/s and seven subjects/group will allow for 80% power to detect this change **Table 2**. With regard to fructose restriction, our preliminary

Treatments	Power	Alpha	Change PWV	SE of Δ in PWV	# of subjects
Allopurinol	90%	0.05	0.6 m/s	0.4 m/s	9
	80%	0.05	0.6 m/s	0.4 m/s	7
Low-fructose	90%	0.05	0.5 m/s	0.4 m/s	13
	80%	0.05	0.5 m/s	0.4 m/s	10

Table 2

data demonstrate a significant improvement in PWV only in the females. We anticipate that the reduction in PWV with diet may be smaller than that with allopurinol. We would need 13 subjects/group to detect a 0.5 reduction in PWV with 90% power; 10/group would give 80% power. Further, as we do not expect changes in the PWV during 6 month of follow up in the placebo group and to accommodate variability in response and potential dropout, we will include 40 subjects in the low-fructose intervention, 40 subjects in the allopurinol cohort and 20 in the placebo group (half men and half women for all the cohorts). Further and based in our previous weight loss/dietary intervention⁶⁹, we have chosen a sample size to be able to detect a reduction in PWV of 0.6 m/s of 20 diabetic males and 20 diabetic females.

VII. STUDY PROCEDURES/ DESIGN/TREATMENT PLAN

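### Section VI sizes the trial partly to show larger PWV effects in women, but Aim 2 has no sex comparison, neither named test makes one, and Table 2 does not say which contrast its power describes

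*Combined protocol and SAP*

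**What the plan says.** Section VI states the sizing goal for Aim 2: "i.e. to show that XO inhibition and fructose restriction reduce PWV, and that these interventions are more effective in women than in men". It then names the tests: "Calculations are based on the paired *t*-test for pre- to post-treatment change, and independent *t*-tests for comparisons between treatment arms", with two-sided alpha 0.05 for both.

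Section I.B words Aim 2 differently: "To assess whether XO inhibition is superior to dietary-induced SUA reduction in ameliorating arterial stiffness in T2D subjects". Sex appears in Aim 1, whose hypothesis is that the link between stiffness and uric acid, oxidative stress, endothelial dysfunction and inflammation "seen in T2D women will be weaker or absent in men". That concerns an association, not response to treatment. Section I.A does list sex-specific treatment effects as a gap the study will close, but names no test for them.

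On power, Section VI says: "Nine subjects per group (9 men and 9 women) completing the allopurinol arm will allow for 90% power to detect a change" of 0.6 m/s, with seven per group for 80%. For low fructose it gives 13 and 10 per group for 0.5 m/s. Table 2 enters 0.4 m/s in every row under "SE of Δ in PWV". Part 3 is sized to detect "a reduction in PWV of 0.6 m/s of 20 diabetic males and 20 diabetic females", with no SD, power or test given.

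**The concern.** A stated sizing goal has no matching objective, test or assumed difference. The aims do not contain it, the named tests do not address it, and Table 2 could describe a pre-post change, a comparison of arms or a comparison of the sexes.

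The gap affects what could be reported. With no contrast named in advance, a claim about sex could rest on one p-value in women and another in men, and significance in one sex but not the other does not test a difference. Suppose, as an assumption, a true reduction of 0.2 m/s in both sexes, SD of change 0.4 and 18 completers per sex. Each paired t-test then has 51.6% power, so the chance of significance in women but not in men is 0.516 x 0.484 = 25%, although no sex difference exists.

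The direct contrasts also differ widely in precision, so a choice made after seeing the data would matter.

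**Working it through.** **Inputs.** From Section VI and Table 2: two-sided alpha 0.05; reductions of 0.6 m/s (allopurinol) and 0.5 m/s (low fructose); variability 0.4 m/s; planned numbers of 40 allopurinol, 20 placebo and 40 low fructose, half of each sex. Part 3 has 20 men and 20 women. Section III.A allows 10% dropout, so 20 per sex becomes 18 and 10 becomes 9. The documents give no assumed women-minus-men difference, so ranges are shown.

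**Step 1: reproduce Table 2.** Per group, n = 2 x ((z0.975 + z_power) x 0.4 / delta)^2.

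| delta (m/s) | Power | Formula | Stated n |
|---|---|---|---|
| 0.6 | 90% | 9.34 | 9 |
| 0.6 | 80% | 6.98 | 7 |
| 0.5 | 90% | 13.45 | 13 |
| 0.5 | 80% | 10.05 | 10 |

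Rounded to the nearest integer, all four rows match. A paired t-test with SD 0.4 would need 7, 6, 9 and 8. The arithmetic therefore points to two independent groups with 0.4 used as an SD. It does not identify the two groups.

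**Step 2: power of the named tests at the stated n** (noncentral t, SD 0.4).

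| n | delta (m/s) | Stated | Paired t, SE = 0.4/sqrt(n) | Two-sample t, SE = 0.4 x sqrt(2/n) |
|---|---|---|---|---|
| 9 | 0.6 | 90% | 97% | 85% |
| 7 | 0.6 | 80% | 91% | 73% |
| 13 | 0.5 | 90% | 98% | 86% |
| 10 | 0.5 | 80% | 94% | 75% |

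Neither named test gives the stated power in any row.

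**Step 3: women versus men within one arm, change scores, SD 0.4.**
- 20 v 20: SE = 0.4 x sqrt(2/20) = 0.126; detectable at 80% power 0.36 m/s.
- 18 v 18: SE = 0.4 x sqrt(2/18) = 0.133; detectable 0.38 m/s. Power is 99% for a difference of 0.6, 95% for 0.5 and 59% for 0.3.

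**Step 4: placebo-controlled treatment-by-sex interaction in Part 2, change scores, SD 0.4.** SE = 0.4 x sqrt(2/nT + 2/nP), where nT and nP are drug and placebo subjects per sex.
- 20/10: SE = 0.4 x sqrt(0.3) = 0.219; detectable 0.62 m/s; power 77% for 0.6 and 27% for 0.3.
- 18/9: SE = 0.4 x sqrt(0.333) = 0.231; detectable 0.66 m/s; power 72% for 0.6 and 25% for 0.3.

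**Step 5: dependence on 0.4.** Detectable differences are proportional to the SD. At an assumed SD of 0.8 they double, to 0.73-0.77 m/s within an arm and 1.25-1.32 m/s for the interaction. If 0.4 is a true SE at n = 9, the SD is 0.4 x sqrt(9) = 1.2. Power for a 0.6 m/s difference is then 31-34% within an arm and 14-15% for the interaction.

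**The case against.** The strongest reply is that Table 2 already is a women-versus-men calculation. It matches a two-group formula, the groups are described as 9 men and 9 women, and the paragraph opens with a sex rationale. That reading is plausible. But 0.6 and 0.5 m/s would then be differences between the sexes, whereas the text presents them as reductions in PWV, and it never says that the sexes are being compared. The ambiguity stands, though clarifying it takes little.

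Three stronger readings are tempting, and the documents do not support them.
- A reader might infer that the trial is too small. If the SD of change is 0.4 and men do not respond, the within-arm contrast has 95-99% power at 18 v 18 for the assumed effects. If placebo PWV is stable in both sexes, and Section VI expects no change on placebo, that contrast and the interaction estimate the same difference in Part 2. The roughly 1.7-fold larger detectable difference for the interaction (0.62/0.36) is the price of not relying on that expectation.
- A reader might infer that the plan intends to judge sex differences by significance within each sex. The remark that "data demonstrate a significant improvement in PWV only in the females" describes preliminary results, not a decision rule. The plan leaves room for such a rule but does not state it.
- A reader might infer that the SE label is merely a slip for SD. Reproducing Table 2 shows how 0.4 was used, not what it is. If it is a genuine SE, relabelling it would hide a sizing error.

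It can also be objected that baseline adjustment is unsafe in the diet arms. This is correct. Sex is not randomised, and Section VI cites higher PWV in women with T2D than in men with T2D. Adjusted and change-score contrasts would then differ by (1 - b) times the baseline gap, where b is the baseline slope. With assumed values b = 0.5 and a gap of 0.5 m/s, that is 0.25 m/s. The problem does not carry over to the Part 2 interaction, where treatment is randomised and the baseline gap is common to drug and placebo.

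**Conclusion.** The concern holds in a limited form. Section VI attributes to Aim 2 a sex goal that Aim 2 does not contain, names no test of it, and reports power that neither named test delivers at the stated n. The Table 2 figures rest on 0.4 having been used as an SD, which the exact match in all four rows supports. Whether 0.4 is an SD remains unverified, and every detectable difference above depends on it. Adequacy of the planned N for the sex question cannot be judged until the contrast, the assumed difference and the SD are stated. Certainty is high on the textual mismatch and the missing test, and conditional on the SD for the sizes.

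**What to change.** 1. Reconcile Section VI with Aim 2: either state a sex difference in treatment response as an objective, or remove it from the sizing rationale.
2. If it is kept, in Part 2 test a treatment-by-sex term in a model of 6-month cfPWV adjusted for baseline cfPWV, and report the estimate with its 95% CI.
3. In Parts 1 and 3, compare women with men directly on change in cfPWV. Make the unadjusted change score the main contrast and label it as uncontrolled.
4. Do not base the sex claim on separate within-sex p-values. Keep the paired t-test for the pre-post goal.
5. Trace the source of 0.4, say whether it is an SD or an SE, say which contrast Table 2 sizes, and restate n or power for that test.
6. State the detectable sex difference at 80% power for each contrast, with its SD assumption. If the precision of the placebo-controlled contrast is not acceptable, call it exploratory.

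The cost is wording in Section VI and Aim 2, one model term in Part 2 and one direct contrast per diet arm. The downside is a less favourable stated power for the sex question.

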Following screening, eligible male and female subjects will be assigned to one of the three treatment arms. In the medication arm of the study, they will be randomized to either the allopurinol group (n=40; 20 men and 20 women), or the placebo (n=20; 10 men and 10 women) for 6 months, with a final drug/placebo allocation ratio of 2:1 using a permuted block design with random variation of block size. In the isocaloric low-fructose arm of the study, 20 women and 20 men will be recruited to enter a dietary treatment of fructose restriction for 6 months. In the hypocaloric low-fructose arm of the study, 20 women and 20 men will be recruited to enter a dietary treatment of calorie and fructose restriction for 6 months.

A. Screening/Initial Consenting Visit

The first visit to the CRC will take approximately 6 hours and include a written consent to be screened. The subject is instructed to hold their glucose lowering AM medications (subject will resume regular medications after blood has been drawn), and not to eat or drink anything besides water for at least 10 hours before this visit. The subject is also told not to exercise the morning of this visit. After signing the screening consent form, medical information is obtained by the study team, including: DOB, gender, ethnic/racial category, height, body weight (history of body weight gain or

[figure not shown]

Figure 8. Order of events at the Screening Visit occurring at the clinical research center (CRC).

loss), waist circumference, vitals, and a medical history questionnaire. A fasting blood draw is taken to test for biochemistries. Subjects will also undergo a DEXA scan and vascular measurements including carotid intima media thickness (cIMT), carotid femoral pulse wave velocity (cfPWV), Glycocheck, Near-Infrared Spectroscopy (NIRS), Brachial artery FMD, popliteal artery FMD testing, and OGTT with femoral artery blood flow (**Figure 8**).

An introduction to the clinical trial will be done which includes abbreviated descriptions of the various treatment arms and the placebo arm (no treatment). As soon as the blood biochemistry results are available, the subject is contacted, provided with a copy of the results. If eligible for the allopurinol/placebo arm or (isocaloric) low fructose diet intervention arm, study staff discuss with him/her whether they would like to be consented for enrollment in one of the present studies.

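### Part 2: Section VI does not commit the drug claim to the randomised placebo comparison, and no placebo-controlled sex contrast is tested or powered

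*Combined protocol and SAP*

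**What the plan says.** Section VI (Number of Subjects) gives the sample size two purposes: "i.e. to show that XO inhibition and fructose restriction reduce PWV, and that these interventions are more effective in women than in men". It then names two tests, at two-sided alpha 0.05: "Calculations are based on the paired *t*-test for pre- to post-treatment change, and independent *t*-tests for comparisons between treatment arms". Neither is called primary, and the arms are not identified. There is no separate analysis section. Section V mentions covariate analysis for concomitant medications, and Section VII.F says estrogen will serve as a covariate. Neither gives a model or refers to baseline PWV.

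The drug question is sized as follows: "Nine subjects per group (9 men and 9 women) completing the allopurinol arm will allow for 90% power to detect a change" of 0.6 m/s. The placebo group enters only through an expectation, "as we do not expect changes in the PWV during 6 month of follow up in the placebo group", for which no source is given. No allopurinol-placebo difference, placebo variability or power is stated.

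The word arm is used in two ways.

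- Section VII says that subjects "will be assigned to one of the three treatment arms" and that, within the medication arm, "they will be randomized to either the allopurinol group (n=40; 20 men and 20 women), or the placebo (n=20; 10 men and 10 women". Section IV.B likewise treats "the allopurinol/placebo treatment arm" as one unit.
- Section VII.A promises "abbreviated descriptions of the various treatment arms and the placebo arm (no treatment", which calls placebo an arm but sets it beside the treatment arms. Sections IV and VIII.A also refer to control or placebo as an arm.

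Section VII.K blinds Part 2 and gives the subjects-as-their-own-control argument only for the diet studies.

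**The concern.** Part 2 contains the only randomised control in the trial. If the drug effect is judged from change within allopurinol, that control does no work. A background fall in PWV from regression to the mean, trial participation or changes in other treatment would pass as drug benefit, and a background rise would hide one. The wording of the drug sizing leaves this route open.

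The second purpose, a larger effect in women, needs the drug-minus-placebo difference to be compared between the sexes. Comparing women with men inside the allopurinol group cannot separate a sex difference in drug response from a sex difference in background change. The reader cannot tell from Section VI how much power the placebo-controlled comparison has.

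**Working it through.** **Inputs.** Two-sided alpha 0.05; effects of 0.6 and 0.5 m/s; 0.4 m/s variability, labelled SE (Section VI, Table 2). Allopurinol 20 men and 20 women, placebo 10 and 10 (Section VII). Dropout 10% (Section III.A), giving 18 and 9 per sex. Assumptions: 0.4 is the SD of the change, with 0.8 and 1.0 as a range; variability is equal across groups.

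**Step 1: reproduce Table 2.** The two-group normal formula is n per group = 2 × (1.96 + z)² × (0.4/d)².

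| d (m/s) | Power | Two-group formula | Table 2 | Exact paired t-test |
|---|---|---|---|---|
| 0.6 | 90% | 9.34 | 9 | 7 |
| 0.6 | 80% | 6.98 | 7 | 6 |
| 0.5 | 90% | 13.45 | 13 | 9 |
| 0.5 | 80% | 10.05 | 10 | 8 |

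Rounded to the nearest integer, the two-group formula gives the printed figures; the paired t-test does not. So the arithmetic compares two groups while the text speaks of a change. If the groups are men and women on allopurinol, a sex difference is sized without placebo control. If they are allopurinol and placebo, the sex difference is not sized.

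**Step 2: what the paired test would do without a drug effect.** With n = 40 on allopurinol, SE = 0.4/√40 = 0.063. Against an assumed background fall of 0.2 m/s (noncentrality 0.2/0.063 = 3.16, 39 df), the test is significant 87% of the time; for 0.1 m/s, 34%.

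**Step 3: power of the placebo-controlled contrasts, before baseline adjustment (noncentral t).**

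- Arm-by-sex interaction: SE = SD × √(2/20 + 2/10). At SD 0.4 this is 0.219 with 56 df. After dropout it is 0.4 × √(2/18 + 2/9) = 0.231 with 50 df.
- Sex-averaged allopurinol versus placebo: half of that, 0.110 (0.115 after dropout).

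Figures in brackets are after 10% dropout.

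| SD of change | Drug effect 0.6 | Interaction 0.6 | Interaction 0.3 |
|---|---|---|---|
| 0.4 | over 99% (over 99%) | 77% (72%) | 27% (25%) |
| 0.8 | 77% (72%) | 27% (25%) | 10% (10%) |
| 1.0 | 58% (53%) | 19% (17%) | 8% (8%) |

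At SD 0.4 the 95% CI half-width for the interaction is 0.44 (0.46) m/s.

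**Step 4: baseline adjustment.** With equal variances at both visits and baseline/month-6 correlation r, the residual variance is the change variance × (1 + r)/2. At SD 0.4 and an assumed r of 0.7, interaction power for 0.6 m/s rises to 83% (79%). For r from 0.9 down to 0.5 it is 79–87% (74–84%).

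**Step 5: price of placebo control for the sex question.** Women versus men within allopurinol: SE = 0.4 × √(2/20) = 0.126, power 99.6% for 0.6 m/s. The placebo-controlled SE is √0.3/√0.1 = 1.73 times as large.

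**Step 6: if only women respond (0.6 versus 0 m/s).** The sex-averaged effect is 0.3 m/s, with power 77% at SD 0.4 and 27% at SD 0.8. Allopurinol versus placebo in women alone (20 versus 10, SE 0.4 × √(1/20 + 1/10) = 0.155, 56 df) has 97% at SD 0.4.

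**Step 7: two unranked contrasts.** If either could support a claim at 0.05, the chance of at least one false claim is about 1 − 0.95² = 9.75%.

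**The case against.** The strongest reply is that the comparator is evident. Part 2 is randomised 2:1 and blinded, independent t-tests between arms are named, several sections call placebo an arm, and only the diet studies use subjects as their own control. A plain 40-versus-20 t-test on change would be valid and has over 99% power for 0.6 m/s at SD 0.4. Much of this stands. A reader might infer that the plan means to ignore placebo and judge allopurinol by its pre-post change. The documents do not say that; they leave the choice unmade.

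A reader might also infer that the sex goal has no effect size or power at all. That goes too far. Table 2's arithmetic is two-group and the text puts 9 men and 9 women in the groups, so a 0.6 m/s sex difference on allopurinol may be what was sized. The same words can equally mean a change within each sex. On neither reading is placebo involved.

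It is also fair to say that adjustment is foreseen for medications and estrogen, that Section VI concerns sample size, and that the protocol expects a stronger response in women, so a sex-averaged primary contrast is not the obvious choice. The ranking belongs to the investigators. What remains is that no document says which comparison supports the drug claim.

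**Conclusion.** The point holds in this form: the documents lean towards placebo as comparator but do not commit to it, and the drug sizing is worded as a change on allopurinol. No placebo-controlled sex contrast is tested or powered on any reading of Table 2. The design can answer the drug question. At SD 0.4 the randomised contrast has ample power for 0.6 m/s, and power falls to 77% at SD 0.8 and 58% at SD 1.0. The placebo-controlled sex contrast is much weaker and is best reported as an estimate with its interval.

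All power figures rest on reading 0.4 as an SD although Table 2 labels it SE, so none should enter the protocol unconditionally until that is settled. The 87% figure depends on an assumed drift; nothing in the documents shows that such a drift will occur. This should be fixed before analysis, but it is not a fatal defect.

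**What to change.** For Part 2:

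1. Base the drug claim on allopurinol versus placebo in all randomised subjects as allocated. Model month-6 cfPWV with baseline cfPWV, arm, sex and arm-by-sex. Make within-arm paired tests descriptive. State how missing month-6 values are handled and whether randomisation is stratified by sex; Section VII gives equal numbers by sex but does not mention stratification.
2. Judge the claim of a larger effect in women by the arm-by-sex term with its 95% CI, alongside the allopurinol-versus-placebo estimate in each sex. State in advance which contrast is primary. The sex-averaged contrast is one reasonable option; its weakness if only women respond is shown above.
3. In Section VI, name the groups that Table 2 compares and settle whether 0.4 is an SE or an SD. Then give power for the drug effect and the interaction conditional on that answer, with the range tabulated above.

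The cost is protocol wording and one model. No patients, visits or measurements are added, because PWV is already taken at the baseline and final visits (Sections VII.B and VII.D). The statistical price is the wider standard error of the placebo-controlled sex contrast. The diet arms and the drug-versus-diet comparison of Aim 2 are not addressed by this change.
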